Obesity in the United States is now a well-recognized epidemic with approximately 29% of pregnancies complicated with a BMI > 30 and increasing steadily¹. A retrospective study found delivery costs to be significantly higher in obese women compared to their normal BMI cohort⁹. Obesity in pregnancy is characterized by increased rates of pre-gestational and gestational hypertensive disorders, diabetes, and growth abnormalities¹⁰, leading to increases in medically indicated inductions. Intrapartum, obesity has been linked to increased rates of prolonged latent phase, which is associated with increased rates of cesarean and operative deliveries, hemorrhage, and chorioamnionitis¹¹⁻¹⁷. In a NICHD funded MFMU network study in 2018 examining the length of the latent phase of labor in women undergoing induction, approximately 96.4% of women reached active phase by 15 hours. However, when comparing to non-obese women, the first stage of labor was noted to be significantly longer in duration with a slower progression for both nulliparous and multiparous obese women¹⁸.

Misoprostol is a commonly used agent utilized for cervical ripening that may be administered orally, buccally, or vaginally. There exists a number of dosing and route combinations, however 25mcg vaginally is the most commonly used. ACOG also states that higher doses (such as 50mcg) may be appropriate in some clinical situations¹⁹. Thus, both 25mcg and 50mcg of vaginal misoprostol have been used as the standard of care across the United States. A meta-analysis by Sanchez-Ramos in 2002 pooled results from 5 RCTs comparing the safety and efficacy of 25mcg versus 50mcg of intravaginal misoprostol dosing²⁰. This systematic review demonstrated a significantly greater efficacy with 50mcg dosing (shorter time to delivery, greater proportion of deliveries within 24 hours, and less frequent oxytocin use). While tachysystole occurred more frequently in the 50mcg dosing group, maternal/neonatal outcomes were similar between both groups. However, there was no examination of differences in dosing by BMI category.

Compared to normal weight women, obese women have lower rates of contractions after misoprostol administration than their normal BMI cohort²¹. This suggests a lower bioavailability of misoprostol in women with a large volume of distribution thereby impacting the efficacy of misoprostol. Therefore, obese women may reasonably need a higher dose of misoprostol compared to normal weight. Comparisons between vaginal and oral misoprostol regimens in obese women demonstrate a lower rate of cesarean deliveries²²⁻²³. In fact, Sherwin et al, described a retrospective cohort in 2016 of 483 obese women undergoing induction of labor with either 25mcg or 50mcg of vaginal misoprostol. Time to delivery was significantly shorter when 50mcg dosing was used compared to 25 mcg²⁴. This comparison,

however, has not been studied in a randomized controlled fashion, and the most common dosage of misoprostol remains 25mcg vaginally regardless of maternal BMI. We aim to determine if 50mcg (compared to 25 mcg) of vaginal misoprostol reduces the time from induction start to delivery in obese women.

Obese women are known to have longer induction times, greater failed induction rates, and higher rates of cesarean deliveries, all of which are known to increase maternal and neonatal morbidity. Therefore, appropriate interventions aimed to reduce these consequences are warranted. If this study demonstrates a reduction in time from induction to delivery of three hours, this could potentially result in an estimated 3.1M hours saved on labor and delivery in the United States¹. With the average cost of a vaginal delivery in the United States ranging from \$5000-\$11000²⁵⁻²⁶, this could potentially translate to a savings of up to \$1.89B in labor and delivery hours saved in the United States.

Methods

Study Design:

Double-blind, Randomized Controlled Trial

Study Site:

Ascension Seton Medical Center is a non-profit, private hospital with a level IV maternal care designation that experiences approximately 5000 deliveries a year. Ascension is the primary obstetrical teaching site for the University of Texas at Austin Dell Medical School. The Labor & Delivery ward is a mix of private obstetrical practices and an academic/public teaching component, thus representing a diverse patient population generalizable to the obstetric community as a whole. The academic service is primarily managed by the house staff, midwives, and faculty. This service is comprised of a patient population from the University of Texas at Austin Women's Health Department, CommUnity Care Health Centers, and Ascension Medical Group. The cervical ripening methods employed on labor and delivery consist of a mix of various misoprostol route administrations often times with co-administration of mechanical methods (Cook Balloon) as well. The most commonly employed cervical ripening method involves placement of 25mcg of vaginal misoprostol into the posterior fornix every 4 hours for up to 6 maximum doses. The decision to utilize mechanical ripening, transition to Oxytocin, artificial rupture of membranes, and route of misoprostol administration is at the discretion of the house-staff and faculty on service. However, at this time there does not exist any delineation of cervical ripening methods based on maternal BMI at admission.

Participants:

All patients admitted to Labor & Delivery at Ascension Seton Medical Center will be screened against the inclusion and exclusion criteria by research staff. Eligible patients will be approached by study staff. If interested, the patient will be consented for the study and randomized to either fifty micrograms of vaginal misoprostol dosing (intervention) or twenty-five micrograms of vaginal misoprostol dosing (control) for induction of labor.

Study Criteria:

Inclusion Criteria:

- 1. Singleton gestation
- 2. Age 18 years or older
- 3. Gestational age >= 36 weeks
- 4. BMI \geq 30 kg/m² at time of labor induction
- 5. Cephalic presentation (including successful external cephalic version)
- 6. Cervical dilation <= 3cm
- 7. Intent to proceed with cervical ripening

Exclusion Criteria:

- 1. Contraindication to vaginal delivery (placenta previa, vasa previa, prior classical cesarean, non-vertex presentation, etc.)
- 2. Contraindication to prostaglandin administration (significant allergy, prior cesarean delivery, etc.)
- 3. Multiple gestations
- 4. Gestational age < 36 weeks
- 5. Non-reassuring fetal heart tracing
- 6. Evidence of clinical chorioamnionitis
- 7. Significant vaginal bleeding with concern for abruption
- 8. Prior cesarean delivery or uterine surgery
- 9. Major fetal anomaly or demise
- 10. Cervix >3cm
- 11. No intention to proceed with cervical ripening (not indicated, favorable bishop score, plan for Oxytocin administration, etc.)
- 12. Uterine tachysystole (defined as >= 5 contractions within a 10m period)
- 13. Fetal Growth Restriction (EFW <= 5% or elevated/absent/reversed Umbilical Artery dopplers)
- 14. Inability to give consent (inability to read/write in English or Spanish)

Safety Data

Prior Studies of Safety

- 1. Sanchez-Ramos 2002 meta-analysis reviewing RCTs to compare the safety and efficacy of 25mcg versus 50mcg of intravaginal misoprostol for cervical ripening and labor induction²⁰. This study included a total of 933 women, of which tachysystole occurred in 41 versus 98 women receiving 25mcg versus 50mcg of misoprostol respectively (OR 0.36, CI 0.24-0.53). Cesarean for FHR abnormalities occurred in 25 versus 37 women (OR 0.66, CI 0.39-1.14). APGAR scores less than 7 at 5 min occurred in 8 versus 15 neonates (OR 0.54, CI 0.22-1.28). NICU admissions occurred in 22 versus 36 neonates (OR 0.60, CI 0.34-1.06).
- 2. Farah in 1997 performed an RCT to compare the safety and effectiveness of intravaginal misoprostol at 25mcg versus 50mcg dosing²⁷. This study included 399 patients in total. Tachysystole occurred in 15.6% versus 32.8% of participants (p = 0.0001), however cesarean deliveries occurred in 12% versus 15.9% of women which was non-significant. Umbilical cord pH, APGAR scores < 7, and NICU admissions were also non-significant between the groups. Maternal complications such as hemorrhage and endometritis were non-significant between groups.

3. Diro in 1999 randomized women to either 25mcg versus 50mcg of intravaginal misoprostol to compare the efficacy and safety for cervical ripening and labor induction²⁸. This study included 251 participants of which hyperstimulation was significantly higher in the 50mcg regimen (19 versus 7.2%, p = 0.005), however cesarean delivery was non-significant between both groups. Fetal APGAR scores were non-significant between both groups (8.5 versus 8.4). No other maternal or fetal complications were recorded in the study.

Data Safety Monitoring Board

A Data Safety Monitoring Board (DSMB) will be formed and consist of three individuals: a Maternal Fetal Medicine specialist with expertise in biostatistics ([name]), Obstetrician & Gynecologist ([name]), and Pediatrician/Neonatologist ([name]). These individuals are not involved with the study design nor have potential authorship of the manuscript. The primary purpose of the DSMB will be to monitor patient safety. Additionally, they will have the opportunity to review data collected to monitor the feasibility of the study.

Medication

The patient will be consented for the study and randomized to either fifty micrograms of vaginal misoprostol dosing (intervention) or twenty-five micrograms of vaginal misoprostol dosing (control) for induction of labor. Misoprostol, or Cytotec®, is a synthetic prostaglandin E_1 analog utilized for labor induction purposes and is considered the standard of care in the United States and endorsed by the American College of Obstetrics and Gynecologists¹⁹. A number of different routes and doses exist for misoprostol administration⁶, however 25mcg and 50mcg vaginally are both considered the standard of care for labor induction in the United States.

Consent

Patients who meet inclusion criteria will be identified upon admission to Labor & Delivery at Ascension Seton Medical Center. Study staff will identify qualifying subjects and introduce the study in addition to confirming eligibility. If interested, the patient will be consented for the study by the research nurse or co-investigator. Patients will be randomized to either fifty micrograms of vaginal misoprostol dosing (intervention) or twenty-five micrograms of vaginal misoprostol dosing (control) for induction of labor. If the patient is randomized to the intervention, house staff or a co-investigator will place the vaginal misoprostol per the detailed plan below.

Blinding

Blinding will be achieved by providing misoprostol dosing in prepackaged, numbered envelopes. At randomization, a study number will be assigned and the matching envelope used for misoprostol doses. Misoprostol will be provided as quarters of a whole tablet, using 100 mcg quarters to provide 25 mcg dosing and 200 mcg tablet quarters to provide 50 mcg dosing. When quartered, the 100 and 200 mcg tablets are virtually identical with no distinguishing markings.

Design Protocol

Prior to Randomization

1. Documentation of digital cervical exam prior to randomization.

- 2. Standing weight and height obtained upon admission by standardized designated study scale.
- 3. Review eligibility criteria and confirm patient remains eligible for the intervention.
- 4. Obtain patient questionnaire regarding factors influencing decision to enroll or not enroll in study.
- 5. Consent patient.

Randomization Procedure

After consents are signed, patient will be entered into RedCAP database and randomized. RedCAP will generate a study number. Study team will pull matching envelope from Pyxis with study drug in appropriate blinded dosing.

At Time of Randomization

- 1. Placement of misoprostol dose by House Staff in posterior fornix with documentation of time
- 2. Continuous fetal monitoring and tocodynamometry as per usual care after misoprostol placement.
- 3. Repeat digital cervical exam 4 hours after initial dose
- 4. If the cervical exam remains <= 3cm and the intent remains to continue with cervical ripening
 - a. Proceed with next dose of misoprostol if fetal heart tracings remain Category I, no evidence of continued uterine tachysystole with administration, no significant vaginal bleeding, etc.
 - b. Do not proceed with subsequent dose if fetal heart rate tracings are Category II/III, continued uterine tachysystole is observed, significant vaginal bleeding with concern for abruption is witnessed, new contraindications to vaginal delivery arise.
 - c. If unable to proceed with misoprostol given the above criteria has been met, proceed with usual labor management protocols at the discretion of the provider.
 - d. The provider may choose to initiate resuscitative measures (oxygen, maternal repositioning, IV fluid bolus, etc.) and wait up to 60 minutes to attempt to give a subsequent dose. However, no other dosage or forms (buccal, oral, etc.) of misoprostol should be given other than the randomized allocation.
- 5. Review of fetal heart rate tracings and uterine activity with documentation every hour.
- 6. Repeat steps 1-4 every 4 hours for either a maximum of 6 doses or a maximum of 24 hours has elapsed since the initiation of the first dose, whichever is first.
- 7. If unable to further proceed with misoprostol, usual labor management protocols should be followed at the discretion of the provider.
- 8. Administration of mechanical induction methods (foley balloon, cook balloon, etc.) at the discretion of the provider.
- 9. Usual labor and delivery management protocols should be followed by the provider. Usual indications for failure of induction, failure to progress, and second stage arrest should be followed. Although not mandated, it is suggested to providers that women should be allowed at least 18 hours in the latent phase after completion of any ripening, rupture of membranes, and use of oxytocin before considering the induction "failed" and proceeding to cesarean delivery absent any acute maternal or fetal indications.

- 10. Route of delivery and indication for cesarean up to the discretion of the provider.
- 11. Following delivery, universal cord gas collection (arterial, and/or venous) will be collected for all participants
- 12. Postpartum patients will be asked to complete a survey regarding their satisfaction with their cervical ripening method, prior to discharge from the hospital.

Outcomes

Primary Outcomes

1. Interval time from labor induction initiation to delivery (vaginal or cesarean)

Secondary Outcomes

- 1. Interval time from labor induction initiation to complete cervical dilation
- 2. Interval time from labor induction to vaginal delivery
- 3. Vaginal Deliveries
- 4. Cesarean Deliveries
- 5. Indication for Cesarean Delivery (if applicable)
- 6. Operative Deliveries
- 7. Number of Participants exhibiting Uterine Tachysystole (after 4 hours post-misoprostol)
- 8. Number of Participants exhibiting Uterine Tachysystole with Fetal Decelerations
- 9. Number of Participants receiving Terbutaline
- 10. Number of Participants exhibiting Non-Reassuring Fetal Heart Tracings
- 11. Number of Participants diagnosed with Clinical Chorioamnionitis
- 12. Number of Participants diagnosed with Postpartum hemorrhage
- 13. Composite Maternal Morbidity (ICU admission, Sepsis, Need for Transfusion, Death)
- 14. Composite Neonatal Morbidity (ICU admission, APGAR <=7 at 5 minutes, Sepsis, Acidemia identified upon cord collection (pH < 7.15, Base Deficit >12.0 mmol), Induced Hypothermia, Perinatal Death)
- 15. Patient satisfaction of cervical ripening method as measured by the Six Simple Questions and Visual Analog Pain Scale surveys²⁹⁻³⁰.

Baseline Characteristics

- 1. Maternal Age
- 2. Maternal BMI
- 3. Gestational Age
- 4. Parity
- 5. Race
- 6. Admission Cervical Dilation
- 7. Indication for Labor Induction
- 8. Number of Participants receiving a mechanical method of dilation (foley bulb, cook, etc.)
- 9. COVID vaccination status

Outcome Evaluation

The outcomes will be assessed during the course of the inpatient admission through chart review. The timing of misoprostol placement will be accurately recorded by the nursing staff. Admission, fetal heart

rate tracing review, and delivery times will be recorded by the nursing staff. Adverse outcomes and maternal/fetal complications rates will be recorded prior to hospital discharge by chart review. Given that all outcomes will be evaluated at the time of inpatient admission, there will be no anticipated loss to follow-up.

Randomization

Randomization will occur according to a predetermined computer-generated stratified randomization scheme prepared by a study statistician. This method will be used to achieve balance among the intervention and control groups in terms of patients' characteristics including BMI >= 40 kg/m², parity, and intent to proceed with mechanical dilation at initiation of misoprostol placement. These three variables will be dichotomous such that there will exist a pre-stratified BMI >=40 kg/m² group, BMI <40 kg/m² group, multiparous group, nulliparous group, proceeding with mechanical dilation, and not proceeding with mechanical dilation. A separate block will be generated for each combination of covariates, and patients will be assigned to the appropriate block of covariates. When subjects have been identified and assigned into blocks, simple randomization will be performed within each block to assign subjects to one of the groups (control versus intervention).

Statistical Analysis

Descriptive statistics will characterize the group of individuals recruited to assess comparability of the treatment and control groups. Chi-Square test or Fisher's exact test will be used for categorical variables. Continuous variables will be examined for normality using the Shapiro-Wilk test; normally distributed continuous variables will be compared using the Student's t-test and those non-normally distributed will be compared using the Mann-Whitney U test. Analysis of the primary outcome will consist of a simple comparison of time from labor induction to delivery between the treatment and control group using generalized linear models. Stratified analyses will be used to identify potentially confounding effects. All tests will be two-tailed and use a significant level of <0.05. Data will be analyzed with the intention-to-treat principle.

[figure not shown]
Blinding

This study will be double blinded with the research participants and providers/nursing masked to the interventions. A study statistician will create a randomization scheme as described above which will be utilized by the research pharmacy to distribute pre-packaged masked intervention packets.

Power Analysis

Sample size estimations were conducted using G*Power. Our analyses estimated a medium effect based on a 3-hour difference (SD=6) between our treatment (M=15 hours) and control (M=18 hours) groups⁴. These estimations were derived from the work of Carbone et al, Obstet Gynecol. 2013. We computed the required sample size to detect a medium effect with the specified parameters: strata = 8, power = 0.85, α =.05, f=0.25. This yielded a total sample size of approximately 180 participants total, 90 per group. Figure 1 depicts the relationship between sample size and effect size the study proposed. As effect size decreases, sample size increases.

Figure 1. Relationship between effect size and sample size for MD 30 RCT.

Future Plans

If our results demonstrate that 50mcg of vaginal misoprostol provides shorter interval time to delivery, is safe and well-tolerated, and has similar vaginal delivery rates compared to current induction methods, we will plan to seek funding for a multi-center trial to alter current induction methods for obese patients. This will provide a larger and thus more generalizable patient population to provide guideline recommendation changes.

Budget

To achieve a double-blind study, misoprostol doses will be provided as pre-quartered tablets of either 100 mcg tabs (to achieve 25 mcg) or 200 mcg tabs (50 mcg). These tablets are virtually indistinguishable in size. Ascension Hospital Research Pharmacy has provided significantly discounted rates to provide prepackaged blinded doses of misoprostol to this study. Their estimates include:

- Start-up fees \$1125
- Quarterly Maintenance \$100/month 100% = Agreed to discount for Fellow research project
- Combined Enrollment/Dispensing Fees \$150/subject 50% = \$75 x 180 subjects = \$13,500
- Misoprostol tablets 100mcg x 180 subjects = \$100
- Misoprostol tablets 200mcg x 180 subjects = \$100
- Close-out fees \$200
- Total Estimated Research Pharmacy Fees: \$15,025
- Document Translation Fees: \$500
- Standard medical grade weight scale: \$150 (approximate)
- Participant compensation: \$10 x 180 subjects = \$1800

Projected Total Costs: \$17,475

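### Secondary outcome 5 (cesarean indication) has no stated denominator, and its natural reading is a test within a subset formed after randomization

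*Combined protocol and SAP*

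**What the plan says.** Under Outcomes, Secondary Outcomes, item 5 reads "Indication for Cesarean Delivery (if applicable"). It follows item 4, total cesareans. The entry names no denominator and no test of its own.

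The Statistical Analysis section supplies general rules only: "Chi-Square test or Fisher's exact test will be used for categorical variables", "All tests will be two-tailed and use a significant level of <0.05", and "Data will be analyzed with the intention-to-treat principle". It has no rule for an outcome that is undefined in women who deliver vaginally.

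Under Safety Data, Prior Studies of Safety, item 1, the cited meta-analysis of 25 against 50 mcg is summarized partly by an indication-specific count: "Cesarean for FHR abnormalities occurred in 25 versus 37 women". The trial's own outcome list has no matching count over randomized women.

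**The concern.** An indication exists only if a cesarean took place. Applying the categorical rule to item 5 as listed therefore means testing the distribution of indications among cesareans. Cesarean is itself an outcome (item 4), so the women compared are selected by something that dose may change. Randomization does not protect that comparison.

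The share of cesareans done for a fetal indication depends on two rates: fetal-indication cesareans and all other cesareans. If 50 mcg works as hoped and fewer inductions fail, the fetal share rises with no extra fetal cesareans. If both kinds rise together, the share does not move. Under Future Plans, a multi-center trial depends partly on 50 mcg appearing safe, so a misleading safety comparison could affect that step.

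**Working it through.** **Inputs from the document.** 90 women per arm (Power Analysis: "This yielded a total sample size of approximately 180 participants total, 90 per group"); two-sided 0.05; Fisher's exact test. Prior data: 25 v 37 cesareans for fetal heart rate abnormality among 933 women, OR 0.66. Arm sizes are not given.

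**Assumed.** Every cesarean rate in the scenarios below, and an equal split (466/467) of the 933 women.

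**The document's own figure.** It gives no figure for item 5. The prior odds ratio can be checked under the equal split: (25/441) ÷ (37/430) = 0.66, as stated. The rates are then 25/466 = 5.4% and 37/467 = 7.9%.

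**Why the denominator matters.** Let f be the rate of fetal-indication cesarean and o the rate of all other cesareans, both per randomized woman. The share among cesareans is f/(f + o), so it moves whenever o moves.

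- Same fetal count, fewer others: 9 of 30 cesareans v 9 of 18 gives shares of 30% v 50%. Per randomized woman it is 9/90 = 10% in both arms.
- Both kinds tripled: 5 of 15 v 15 of 45 gives 33% in both arms. Per randomized woman it is 5/90 = 5.6% v 15/90 = 16.7%, Fisher p = 0.031.

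**How often each test rejects.** Each woman is drawn as fetal-indication cesarean, other cesarean or vaginal delivery, with 90 per arm and 20,000 simulated trials per scenario. Ranges show variation between runs.

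| Assumed rates, 25 v 50 mcg | Fetal share | Rejects, cesareans only | Rejects, all randomized |
|---|---|---|---|
| No fetal harm: f 8% v 8%, o 25% v 20% | 24% v 29% | 4–5% | 3% |
| No fetal harm: f 8% v 8%, o 16% v 10% | 33% v 44% | 8% | 3% |
| No fetal harm: f 8% v 8%, o 25% v 15% | 24% v 35% | 9–10% | 3% |
| No fetal harm: f 8% v 8%, o 22% v 10% | 27% v 44% | 18% | 3% |
| No fetal harm: f 8% v 8%, o 25% v 8% | 24% v 50% | 33–34% | 3% |
| Both rise: f 8% v 16%, o 15% v 30% | 35% v 35% | 3–4% | 30% |
| Both rise: f 6% v 18%, o 10% v 30% | 37.5% v 37.5% | 3% | 65% |
| Near the cited data: f 5.4% v 7.9%, total 12% v 15.9% | 45% v 50% | 3% | 6% |

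The last row combines two sources in the safety section: the meta-analysis for fetal-indication cesareans and the 399-patient trial for total cesareans.

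**What the all-randomized comparison can show.** At 5.4% v 7.9% with 90 per arm, the standard error of the difference is √[(0.0536×0.9464 + 0.0792×0.9208)/90] = 0.0371. The 95% CI is then about ±1.96 × 0.0371 = ±7.3 percentage points around a difference of 2.6. Power by normal approximation is Φ(0.0256/0.0371 − 1.96) = Φ(−1.27), about 10%; by Fisher it is about 6%.

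**The case against.** Item 5 is a label, not an analysis. The words in parentheses may only describe a data field left blank after vaginal birth, and the plan states intention-to-treat for all data. A tabulation of cesareans by indication over all women in each arm is also compatible with the text. This stands to the extent that the cesarean-only denominator is an inference. It does not settle the matter: the text leaves the choice open, and the generic categorical rule leads most directly to the restricted test.

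A reader might also infer that item 5 is the trial's main signal of fetal harm, and that harm would disappear from view if the share stayed flat. The document supports neither. It does not rank item 5 or tie a decision to it. Items 8 (tachysystole with decelerations), 10 (non-reassuring tracings) and 14 (neonatal composite) do not depend on cesarean, and cord gases are collected in every participant. Item 4 would also react. When fetal-indication cesareans go from 8% to 16% and others from 15% to 30%, total cesareans go from 23% to 46%, and Fisher on item 4 rejects in about 88% of trials. With items 4 and 5 both reported, the count per randomized woman could usually be recovered. What remains is that none of those items isolates operative delivery prompted by fetal status, and choosing the denominator after seeing results is what prespecification should prevent.

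Finally, the larger false-rejection rates need a steep fall in other cesareans. The one trial whose total rates are quoted shows 12% v 15.9%, higher on 50 mcg. This stands: under modest shifts, or near those rates, the two denominators reject at similar rates.

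**Conclusion.** The point holds as a gap in specification with a better method readily available. Item 5 has no stated denominator, and its natural execution is a non-randomized comparison among cesareans. If it is run that way with no true difference in fetal-indication cesareans, false rejection ranges from close to nominal (4–5%) for a small fall in other cesareans to 33–34% for a fall from 25% to 8%. The all-randomized test stays at about 3%. If both kinds rise in proportion, the restricted test has no power beyond its error rate.

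These sizes rest on assumed cesarean rates; only the 90 per arm, the test and the significance level come from the document. The document does not support saying that the plan definitely restricts the analysis, that item 5 is the chief fetal-safety measure, or that harm would go unseen. The primary analysis and the sample size are unaffected.

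**What to change.** Replace item 5 with two yes/no secondary outcomes, each counted over all randomized women by assigned arm:

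1. cesarean for a fetal heart rate indication;
2. cesarean for failed induction or arrest of labor.

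State how a cesarean with more than one recorded indication is counted. Report each outcome as a risk difference with a 95% CI. Show the mix of indications among cesareans descriptively, with no test.

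The cost is one or two lines of text and one more secondary comparison. No new data are needed, since outcomes already come from chart review (Outcome Evaluation). The change makes the comparison a randomized one and lets it be set beside the cited meta-analysis count. It does not make it precise, so the interval should carry the interpretation rather than the p-value.

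### Receipt of a mechanical method is listed as a baseline characteristic although it can follow randomization; the pre-randomization factor, mechanical intent, is missing from the list

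*Combined protocol and SAP*

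**What the plan says.** All places are in the combined protocol and SAP.

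- Outcomes, Baseline Characteristics, item 8: "Number of Participants receiving a mechanical method of dilation (foley bulb, cook, etc"). This is receipt, not intent. BMI and parity are items 2 and 4; intent is not listed.
- Design Protocol, At Time of Randomization, step 8: "Administration of mechanical induction methods (foley balloon, cook balloon, etc.) at the discretion of the provider". No time limit is given, and steps 3 and 6 provide for a cervical exam every 4 hours.
- Randomization: the three dichotomous stratification factors are BMI at or above 40, parity, and "intent to proceed with mechanical dilation at initiation of misoprostol placement".
- Statistical Analysis: "Descriptive statistics will characterize the group of individuals recruited to assess comparability of the treatment and control groups". Between-arm tests of categorical items are chi-square or Fisher's exact. On the primary outcome: "Analysis of the primary outcome will consist of a simple comparison of time from labor induction to delivery between the treatment and control group", by generalized linear models and under intention to treat. Then: "Stratified analyses will be used to identify potentially confounding effects". No stratifying variable is named.

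**The concern.** A baseline characteristic must be fixed before assignment. Receipt of a balloon is not. Providers see how the cervix responds to the assigned dose and may add a balloon in response. Blinding does not prevent this, because the decision follows progress and not knowledge of the arm. If the 50 mcg dose ripens the cervix faster, fewer women in that arm may receive a later balloon.

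Two consequences follow. First, a chi-square or Fisher test of receipt at the 0.05 level could report an effect of dose as a failure of comparability, while the table says nothing about balance on the third stratification factor. Second, because the confounding analyses have no named variables, an analyst could stratify on receipt. That conditions on a possible consequence of treatment and compares unlike women within strata.

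**Working it through.** **Timing of each variable**

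| Variable | Fixed before assignment? | Can dose affect it? | In baseline list? |
|---|---|---|---|
| BMI | yes | no | yes |
| Parity | yes | no | yes |
| Mechanical intent at initiation | yes | no | no |
| Mechanical receipt, planned at initiation | planned before | no | yes, within item 8 |
| Mechanical receipt, later or changed | no | yes | yes, within item 8 |

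Item 8 mixes the last two rows.

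**Inputs from the plan.** The Power Analysis gives 15 h against 18 h with SD 6, so f = (3/2)/6 = 0.25, as stated. The documents give no balloon rate, no balloon effect on time and no rule for adding one, so there is no plan figure on this point to reproduce. (The sample size of 180 plays no part in the argument.)

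**Assumed inputs, for illustration only.** 30% intend a balloon. Among the other 70%, 40% receive one later at 25 mcg and 20% at 50 mcg. The total dose effect is held at -3 h. The balloon changes time to delivery by b hours. The correlation between early slow response and underlying labour length is r, from 0 to 0.5.

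*Receipt by arm.* 25 mcg: 0.30 + 0.70 × 0.40 = 0.58. 50 mcg: 0.30 + 0.70 × 0.20 = 0.44. The difference is -0.14.

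*Mediation part.* Stratifying on receipt removes b × (-0.14) from the total effect.
- b = -3 h, r = 0: -3 - (-3)(-0.14) = -3.42 h.
- b = +3 h, r = 0: -3 - (3)(-0.14) = -2.58 h.

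*Selection part.* Take b = 0 and r = 0.5. Within each receipt stratum, mean underlying labour length (in SD units, from truncated-normal means) is:
- received: 0.233 (25 mcg) and 0.223 (50 mcg); difference × 6 h = -0.06 h
- not received: -0.322 and -0.175; difference × 6 h = +0.88 h

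The stratum weights are 0.58 × 0.44/1.02 = 0.250 and 0.42 × 0.56/0.98 = 0.240. The weighted bias is (0.250 × -0.06 + 0.240 × 0.88)/0.490 = +0.40 h, so the estimate is -2.60 h.

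*Together* (the parts add, and a simulation of 2,000,000 women per scenario agrees):

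| Balloon effect b | r = 0 | r = 0.3 | r = 0.5 |
|---|---|---|---|
| 0 h | -3.00 | -2.76 | -2.60 |
| -3 h (shortens) | -3.42 | -3.18 | -3.02 |
| +3 h (lengthens) | -2.58 | -2.34 | -2.18 |

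If later receipt is equal by arm (30% and 30%), stratifying on receipt gives -3.00 h. If it is higher at 50 mcg (20% against 30%) and b = -3 h, it gives -2.79 to -2.98 h. Stratifying on intent gives -3.00 h in every scenario.

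**The case against.** The strongest reply has four parts.

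1. *The primary result is safe.* It is an unadjusted comparison under intention to treat, and receipt cannot change it. This stands. A reader might infer that the trial's main estimate is at risk; the documents do not support that.

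2. *The plan does not say it will stratify on receipt.* The confounding sentence neither names variables nor refers to the baseline list, and the only strata defined anywhere are the three pre-randomization factors, which the Power Analysis echoes as eight strata. This stands. A reader might infer that conditioning on receipt is planned; it is only left open. But nothing excludes it, and the label baseline invites it.

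3. *Item 8 may be the intent stratum loosely worded.* The Randomization section calls those strata proceeding or not proceeding with mechanical dilation, and the Study Site section says balloons are often given alongside misoprostol. A balloon planned at initiation is not a consequence of dose. This stands, and it confines the problem to later or changed use. It does not turn receipt into intent.

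4. *The bias need not be toward no difference.* A reader might infer that adjustment for receipt must shrink the effect. One model, in which every balloon is a reaction to slow progress and the link is strong, does give attenuation of about 31 to 52%. Adding an assumed 30% of planned balloons to that model cuts it to about 5 to 26%, and 50% planned to about 1 to 16%. If balloons shorten labour and are used more at 25 mcg, the effect can grow. Neither sign nor size can be taken from the documents.

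**Conclusion.** The point holds in limited form. A variable that can be determined after randomization is classed as baseline, and the pre-randomization factor that belongs there is missing. Following the plan as written would test a possible consequence of dose as evidence of comparability. The unnamed variables of the stratified analyses leave room to condition on it as well.

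The size is illustrative. With the rates assumed above, and a balloon that has no effect or saves 3 h, a true 3 h reduction becomes about 2.6 to 3.4 h. If the balloon lengthened labour by 3 h, the estimate could fall to about 2.2 h. There is no distortion if receipt does not differ by arm. These figures rest on assumed balloon rates, balloon effect and selection, and they bound nothing. What is at stake is the comparability table, the secondary stratified analyses and how the primary result is read beside them.

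**What to change.** 1. Replace Baseline Characteristics item 8 with intent to use a mechanical method at initiation of misoprostol, as recorded for the randomization stratum.
2. Report actual receipt by arm, with timing where charted, as a post-randomization co-intervention, outside the comparability assessment.
3. In Statistical Analysis, state that stratified or adjusted analyses of the dose effect use only pre-randomization variables, namely BMI >= 40, parity and mechanical intent, and do not use actual receipt.

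The cost is wording. Intent must already be captured to assign the stratum, and receipt is already listed for collection. At most, a field for balloon timing is needed if it is not already charted. The sample size, the primary analysis and clinical care do not change.
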